1. BACKGROUND OF THE STUDY

Recent advances in insulin pumps, continuous glucose monitoring (CGM) devices, and control algorithms have resulted in an acceleration of progress in the development of the automated systems of insulin delivery including advanced hybrid closed loop (HCL) insulin pumps. The results of the AHCL insulin pump based studies published so far are very encouraging, including that Medtronic-sponsored study performed at our center “Transition of CSII/CGM naïve patients directly into AHCL (780G) insulin pump: the impact on glucose patterns and quality of life measures” (1-6). Unfortunately there is little data concerning the usage of AHCL systems in older patients. The management of these individuals is particularly challenging as older adults with type 1 diabetes are especially vulnerable to hypoglycaemia. The recent ADA/EASD consensus underlines that the use of advanced technologies in older individuals is useful and should not be discontinued or a priori excluded because of the older age (7). Since the AHCL systems are very effective in hypoglycemia prevention they could be considered the treatment of choice in older patients with T1DM. The open question is how effectively would older individuals adopt this advanced technology, how would they accept it, and if the simplicity in terms of everyday usage of AHCL versus less advanced technologies would be appreciated by older individuals with T1DM. Older people with diabetes have a higher risk for cognitive impairment and for physical disability whether this may be effected by an improvement in glucose indices is unknown. Thus, the aim of this study is to assess the efficacy of AHCL in people with type 1 diabetes in improving glucose indices, quality of life and physical capacity indices.

2. TRIAL DESIGN

[figure not shown]
2.1. Objectives

The primary objective of this study is to evaluate whether the AHCL (MiniMed 780G®) system improves glycemic control and quality of life in older (above 65 years of age) individuals with T1D and if one year ACHL treatment may affect vascular improve of those patients.

2.2. Study design

The trial is a two-centers, randomized controlled, parallel group study. Patients will be followed up during approximatively 12 months, with preliminary evaluation concerning efficacy and safety performed at 6 months.

Figure 1: Study Design

2.3. Visits and Procedures

2.3.1. Run-in Phase

Screening visit:

- Patients' eligibility assessment,
- obtaining of informed consent,
- QoL questionnaire, the WHO-5 questionnaire as well as the General Health questionnaire will be used
- lab tests: HbA1c, eGFR, ASPAT, TSH
- Vascular status : Intima-media thickness-IMT, Flow-Mediated Dilatation -FMD and Laser Doppler Flowmetry- LDF.
- Sarcopenia/functional status/frailty will be assessed using several tools:

1) Well validated tests of balance, strength & aerobic capacity. This will include:

Gait, Balance & Aerobic Capacity Measurement

The following instrument will be used to assess gait speed balance and aerobic capacity

Timed up and Go^{1 2-4}

The objective of this test is to measure the ability of a person to: stand up, walk, turn around and sit down safely in a timely manner. The test examines most mobility skills. The participant is told to get up from a chair with handles, walks 3 meters, turns, walks back, and sit down again. The score is according to the length of time in seconds to complete the task. The score is categorized according to the risk for falls and independent walking. The following cut-offs are conventionally used: less than 14 seconds = independent mobility; 15-20 seconds = semi-independent mobility may have a somewhat increased risk for falls & needs further evaluation some may need a walking aid; 20-30 seconds = dependent mobility: need help walking, 50% with a cane, 40% walker, 10% supervision. Some will need help in transfers, and most will require help using the toilet. Many in this category won't go outside the home alone. Data suggests that the timed "Up & Go" test is a reliable and valid test for quantifying functional mobility that may also be useful in following clinical change over time.

6 min walk^{1,5-7} The six-minute walk test (6MWT) measures the distance an individual is able to walk over a total of six minutes on a hard, flat surface. The goal is for the individual to walk as far as possible in six minutes. The individual is allowed to self-pace and rest as needed as they traverse back and forth along a marked walkway. The six minute walk distance in healthy adults has been reported to range from 400m to 700m. People with lower vs. higher scores on the 6 minute walk are at higher risk for falls, disability, frailty, hospitalization and death.

10 meter walk⁸: The test examines the pace and number of steps it takes a person to pass 10 meters. A route of 10 meters is marked by two lines and a chair is placed two meters past the runway end line. The subject starts the test two meters before the runway and goes 14 meters (two meters for acceleration at the beginning and two meters for deceleration at the end). The score achieved is determined by the time lapsed by the participant during walking along the middle 10 meters. Subject performs the test four times, the first two times are for practice: measurement occurs only during the third and fourths time. In addition to measuring the speed, the number of steps required to cross the short distance are also

counted. Studies have shown that better gait speed is associated with a lower risk for functional decline, hospitalization and mortality.^{9,10}

Berg Balance Scale (BBS): The berg balance test includes 14 tasks which evaluate static and dynamic balance. Each task receives a score of 0 to 4 points - depending on the quality and task execution time.⁴⁰⁻⁴² The maximum score is 56 points. The scores are dichotomized in the following manner:

1. Scores below 36 indicate impairment with an increased risk for falls.
2. Scores between 37-45 indicate need for a walking aid in order to walk in a safe manner.
3. Scores above 45 indicate an independent walker without an increased risk of falls.

The equipment used for the Berg balance test is a step stool, a mat table, a chair with arms, a tape measure, a stopwatch, a pen, and a table. Studies have shown that individuals with scores indicating impaired balance are at increased risk of falls resulting in hospitalizations and deaths.¹¹

Four Square Step Test (FSST)¹²

The test evaluates dynamic balance in a high functional level and features walk forward backwards left and right above 2 90 cm and 2.5 cm high long sticks that divid the floor into four squares. The participant is stands in square 1 facing no. 2 square. The goal is to walk as quickly as possible in all the squares in the following order: from 1 to- 2,3,4,1,4,3,2 and 1 without touching the sticks. The score is the time required to complete the entire route.

Grip Strength

The maximum grip strength is examined utilizing the Jammer dynamometer. The test is conducted in a neutral hand position and repeated three times. The score is the average strength in kg this is compared to the general population according to age and gender.⁴³⁻⁴⁶

30 second chair stand.

The purpose of this test is to assess lower body strength. The participant is required to rise from sitting position with arms crossed as many times as possible in 30 seconds. Scoring is according to the number of stand executed in 30 seconds.⁴⁷

Fried Scale

Frailty is defined as the presence of at list three components.³⁴

- i. Weight loss: "In the last year have you lost more than 10 pounds unintentionally (not due to dieting or exercise)?
- ii. Poor endurance and energy: as indicated by self-report of exhaustion. Self-report exhaustion, identified by two questions from the CES-D scale.
- iii. Low Physical Activity level: kilocalories expended per week, calculated adjusted according to age and gender.
- iv. Walk time: over seven seconds to pass three meters

2) Participants will be asked to install an app developed in-house for the assessment of clinical sarcopenia in older people with diabetes (EFSD grant).

- Cognitive function will be assessed at baseline using the Montreal Cognitive Assessment (MOCA)¹³ and a digital version of the Digital Symbol Substitution Test (DSST)¹⁴

-
-

Run-in phase:

- Patient continues MDI/CSII treatment as per routine procedures
- The patient will be instructed to perform ≥ 4 blood glucose (BG) measurements per day
- Blinded CGM evaluation is performed for 12 days.

Randomization visit:

- BG meter data download, data review and optimization of MDI/CSII management.
- Blinded CGM data download.
- Patients will be randomized to either:
 - MiniMed 780G AHCL system, also referred to AHCL group
 - MDI/CSII

Randomization will be done by Random Allocation Software to allow fair distribution among sites and eliminate place for bias. <http://random-allocation-software.software.informer.com/2.0/>

2.3.2. Study phase

Both groups will have a similar number of visits in order to minimize bias. However, the AHCL group will have 2 additional visits to allow for patients to be trained on the AHCL system.

MDI/CSII group:

The patient continues MDI/CSII treatment as per routine procedures

- Visit 1 (day 0, can be combined with the randomization visit): BG meter data download, data review and optimization of MDI management.
- Visit 2 (Visit 1 + 14 days, window +/- 3 days): BG meter data download, data review and optimization of MDI management
- Visit 3 (Visit 2 + 14 days, window +/- 3 days – month 1): BG meter data download, data review and optimization of MDI/CSII management
- Visit 4 (month 3): BG meter data download, data review and optimization of MDI/CSII management
- Visit 5 (month 6): BG meter data download, data review and optimization of MDI/CSII management, blinded CGM evaluation start. Preliminary evaluation
- Visit 6 (month 9) – *phone call*
- Visit 7 (month 12 minus 14 days) - *phone call*: blinded CGM - sensor change.
- Visit 8 (Visit 6 + 6 days, window +/- 1 day): QoL questionnaire, blood sample for HbA1c lab test, blinded CGM data download, . vascular status : Intima-media thickness-IMT, Flow-Mediated Dilatation -FMD and Laser Doppler Flowmetry- LDF.
-

Study conclusion.

AHCL group:

- Visit 1 (day 0, can be combined with the randomization visit): the patient will get the pre-reading materials on the 780G system, to be read before Visit 2. CGM training and initiation.
- Visit 2 (Visit 1 + 1 day, window +7 days): 780G system training and initiation in Manual Mode.
- Visit 3 (Visit 2 +3 days, window +3 days): 780G system data download. Auto Mode readiness assessment. 780G system initiation in Auto Mode with AHCL control
- Visit 4 (Visit 3 + 3 days, window +1 day) – phone call: Auto Mode initiation follow-up.
- Visit 5 (Visit 4 + 7 days, window +/- 3 days): 780G system data download, therapy assessment and optimization
- Visit 6 (Visit 5 + 14 days, window +/- 3 days, month 1): 780G system data download, therapy assessment and optimization
- Visit 7 (month 3): 780G system data download, therapy assessment and optimization
- Visit 8 (month 6): 780G system data download, therapy assessment and optimization. Preliminary evaluation of efficacy and safety (see primary and secondary endpoints except for vascular status assessment)
- Visit 9 (month 9):
- Visit 10 (month 12): 780G system data download, QoL questionnaire, blood sample for HbA1c lab test, vascular status : Intima-media thickness-IMT, Flow-Mediated Dilatation -FMD and Laser Doppler Flowmetry- LDF.
-
-

Study Conclusion

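### The control arm's final visit is dated before the visit that precedes it, and its end-of-study CGM has no scheduled start

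*Protocol*

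**What the plan says.** Section 2.2 of the protocol plans that "Patients will be followed up during approximatively 12 months", with a preliminary evaluation at 6 months. The later part of the MDI/CSII (control) schedule in Section 2.3.2 then reads:

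- Visit 5, month 6: "optimization of MDI/CSII management, blinded CGM evaluation start. Preliminary evaluation".
- "Visit 6 (month 9": a phone call with no CGM task.
- "Visit 7 (month 12 minus 14 days": a phone call whose task is "blinded CGM - sensor change".
- "Visit 8 (Visit 6 + 6 days, window +/- 1 day): QoL questionnaire, blood sample for HbA1c lab test, blinded CGM data download", together with the vascular measurements. This visit concludes the study for the arm.

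For the AHCL arm, the month-6 visit carries a "Preliminary evaluation of efficacy and safety (see primary and secondary endpoints except for vascular status assessment", and the last visit is "Visit 10 (month 12): 780G system data download, QoL questionnaire, blood sample for HbA1c lab test".

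Section 2.7.2 requires two weeks of blinded CGM in the control arm at the end of the study, done in the same way as the run-in recording. The run-in recording lasts 12 days in Section 2.3.1 and two weeks in Section 2.7.1. Section 2.7.1 also has study staff download the transmitter in the hospital. The primary endpoint in Section 2.6 is the between-group difference in sensor time in range (TIR), with no time point given.

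**The concern.** Taken literally, the control arm finishes before one of its own visits and almost three months before the AHCL arm. That is unlikely to be intended. The more serious problem appears once the cross-reference is corrected: the recording that should supply control-arm TIR still has no start, and the intervals around it do not add up to its stated length.

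Apart from blinded CGM, the control visits list only blood glucose meter downloads, so no other sensor source is named for this arm. If the two centres resolve the schedule differently, control TIR may rest on differing or shortened windows. A window that was never recorded cannot be recovered at analysis, and a statistical analysis plan cannot supply it.

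The month-6 recording has a related gap. It starts at the very visit that carries the preliminary evaluation, which by the AHCL entry includes the primary endpoint. No end or download is listed for it, and the next two control contacts are phone calls.

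**Working it through.** **Inputs.** Visit timings are from Section 2.3.2, the two-week recording from Section 2.7.2, and the 12-day run-in from Section 2.3.1. The total of 40 is from Section 7 (not in dispute here) and the 1:1 allocation from Section 4. Assumption: one month = 30.44 days, so month 12 = day 365.25. With 30-day months the day counts shift by a few days and the conclusions do not change.

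**Visit days**

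- Visit 5: 6 × 30.44 = day 182.6
- Visit 6: 9 × 30.44 = day 273.9
- Visit 7: 365.25 − 14 = day 351.3

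**Reading 1: as written (Visit 8 = Visit 6 + 6 days)**

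- Visit 8: 273.9 + 6 = day 279.9
- Before Visit 7 by 351.3 − 279.9 ≈ 71 days (70 with 30-day months)
- Before month 12 by 365.25 − 279.9 ≈ 85 days (84 with 30-day months)

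The visit order is impossible. It also conflicts with the 12-month follow-up, with CGM at the end of the study, and with the AHCL final visit at month 12.

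**Reading 2: the likely correction (Visit 8 = Visit 7 + 6 days)**

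- Visit 8: 351.3 + 6 = day 357.3 (356.3 to 358.3 with the window), which is 8 days (7 to 9) before month 12. That offset is minor.
- Sensor change to download: 6 days (5 to 7). As a share of 14 days: 6/14 = 43%, range 5/14 = 36% to 7/14 = 50%.
- Start needed for 14 days ending at Visit 8: 357.3 − 14 = day 343.3, which is 8 days before Visit 7.
- Start needed for 12 days: 357.3 − 12 = day 345.3, which is 6 days before Visit 7.
- Listed contacts on or near either day: none. The only study-phase start in this arm is Visit 5, and 351.3 − 182.6 ≈ 169 days before the sensor change. Even the Visit 6 call is 351.3 − 273.9 ≈ 77 days before it.

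**Reading 3: Visit 7 is the start of the final recording**

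- 351.3 + 14 = day 365.3, so a two-week recording ends at month 12 as it should.
- But the Visit 7 task is then a start and not a sensor change, and the 6-day interval to Visit 8 has to become 14 days. Two entries must be rewritten in addition to the visit number.

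No correction of a single entry gives a two-week recording with a start, a sensor change and a download.

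**Participants affected:** 40 × 1/2 = about 20, the whole control arm.

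**The case against.** The best reply is that the intent can largely be recovered. Sections 2.2 and 2.7.2 together place a two-week recording in the last 14 days of a 12-month study, and Visit 7 sits exactly 14 days before month 12. On that view only the sensor-change label and the 6-day interval are out of line. This is a fair guess, but it overrides two explicit instructions. Two 6-day sensor periods would make up the 12-day run-in, so a start six days before Visit 7 is also plausible. The sites should not have to choose.

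It is also fair to say that the 6 days after the sensor change are not the length of the recording, since a change implies a sensor already worn. That stands: the 43% describes what the schedule shows after Visit 7 and is not a forecast of data loss. What is missing is the start.

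Three smaller points stand in part:

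- The study design figure is not available to this review and might show a start contact. It could not remove the conflict in the visit text.
- The preliminary evaluation need not be completed on the day of Visit 5, and a transmitter could be returned without the participant attending. The month-6 gap is therefore real but secondary.
- Section 2.6 gives no time point, so the link between the end-of-study CGM and the primary endpoint is inferred from Sections 2.2 and 2.7.2. It is the only coherent reading.

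**Conclusion.** The concern holds, and the schedule must be corrected. As written, control Visit 8 falls about 71 days before Visit 7 and 85 days before month 12. With the cross-reference read as Visit 7, the end-of-study blinded CGM still has no listed start, and 5 to 7 days to the download are shown against a two-week requirement. All control participants, about 20 of 40, are affected, in the recording that feeds the primary endpoint.

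The conclusion rests on calendar arithmetic with an assumed month length, on the inference that the end-of-study recording supplies control-arm TIR, and on the visit text without the figure. Nothing in the protocol allows a bias in TIR to be computed, and none is claimed. A comparison of control outcomes near month 9 with AHCL outcomes near month 12 would arise only under the literal reading.

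**What to change.** Reconcile Section 2.3.2 (both arms) with Section 2.7.2:

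1. Anchor control Visit 8 to month 12 and give it and AHCL Visit 10 one common window. Visit 10 has none at present.
2. Name the contact at which the final blinded CGM starts, so that the full recording ends at Visit 8, and label Visit 7 as a start or a sensor change to match.
3. State one recording length. Section 2.7.2 refers back to the run-in, which is given both as 12 days and as two weeks.
4. Since Visits 6 and 7 are phone calls, say whether the sensor is supplied beforehand for self-insertion or one of those contacts is made in person.
5. Give the month-6 control recording its own end and a download in time for the preliminary evaluation, or delete it.

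The cost is a short amendment to Section 2.3.2 and a memo to the two sites, with no added participants. For each of about 20 controls it means a sensor supplied in advance or one phone contact made in person. If the month-6 recording is kept, add one transmitter return for download in the hospital.

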2.4. Inclusion criteria

1. Age over 65 years
2. T1DM
3. Willing to participate in a study for the specified duration
4. Willing to perform ≥ 4 finger stick blood glucose measurements daily
5. Willing to wear the system continuously throughout the study
6. Glycosylated hemoglobin (A1C) value less than 10.0% at time of screening visit
7. Treated with MDI/CSII (with exclusion of 780G)
8. Willing to perform at least 4 BGM/day, when on MDI/CSII
9. Lack of advanced complications of diabetes, eGFR>30

2.5. Exclusion criteria

1. Severe concurrent illness
2. Laboratory abnormalities, or medications that might affect study participation,
3. Severe renal impairment (eGFR<30)

4. hemoglobin A1c value above 10%
5. previous treatment with 780G

2.6. Study endpoints

Primary endpoint:

- Between group difference in the percentage of time spent within range with sensor glucose (SG) between 70–180 mg/dL (TIR) (3.9-10.0 mmol/L).

Secondary endpoints:

- Between groups difference in the percentage of participants achieving TIR >70%
- Between group difference in the percentage of time spent:
 - in hyperglycemic range with SG > 250 mg/dL (13.9 mmol/L)
 - in hyperglycemic range with SG > 180 mg/dL (10.0 mmol/L)
 - in hypoglycemic range with SG < 54 mg/dL (3.0 mmol/L)
 - in hypoglycemic range with SG < 70 mg/dL (3.9 mmol/L)

The above 4 endpoints will be also categorized by daytime (06:01 to 23:59) and night-time (00:00 to 06:00).

- Between group difference in the mean glucose level
- Between group difference in the glycemic variability measure by SD and CV
- Between group difference in the HbA1c levels
- Between group difference in the Diabetes Quality of Life (QoL) questionnaire score.
- Differences in baseline vs end of the study in vascular status as measured with IMT, FMD, LDF
- Difference in physical capacity indices listed in screening visit

Safety endpoints:

- Number of severe hypoglycemic episodes
- Number of DKA events
- Number of hospitalisations

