7. STATISTICS CONSIDERATIONS: SAMPLE SIZE CALCULATION AND STATISTICAL ANALYSIS

Statistical Hypothesis

The null-hypothesis $H_0: TIR_{MD/CSII} = TIR_{AHCL}$ will be tested against the alternative hypothesis $H_A: TIR_{MD/CSII} \neq TIR_{AHCL}$, where $TIR_{MD/CSII}$ and TIR_{AHCL} are the mean Time in Range (70–180 mg/dL) in the MDI/CSII and the AHCL groups, respectively.

Sample size

Using data from the study previously performed at our center a mean TIR=80% (Std=15%) in the AHCL group and a mean TIR= 65% (Std=15%) in the MDI/CSII group. For a two sided two-sample t-test, a total sample size of 40 subjects is required to test the hypothesized difference in population means of 15% with a 95% confidence level, 80% power and attrition rate of 15%.

Analysis of primary endpoint

The primary analysis will use a two-sample t-test to compare the mean TIR between the randomized arms of the study. The analysis will be adjust by baseline TIR. The mean TIR in the patients in the AHCL arm will be claimed to be smaller than then mean TIR in the MDI arm if the average TIR is smaller in the AHCL arm and the associated p-value of the test is less than 0.05. No extra adjustments are needed for this nested test.

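### The vascular secondary endpoint is worded as baseline versus end of study rather than as a between-group difference, although both randomised arms are measured at screening and at their final visit

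*Protocol*

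**What the plan says.** Section 2.6 lists one primary and eight secondary endpoint lines. Seven of the nine are worded as differences between groups, for example "Between group difference in the HbA1c levels". The vascular line reads "Differences in baseline vs end of the study in vascular status as measured with IMT, FMD, LDF": the contrast it names is time, and no arm is mentioned. The physical-capacity line that follows names no contrast.

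The vascular question belongs to the primary objective in section 2.1, which asks "if one year ACHL treatment may affect vascular improve of those patients". Section 2.2 describes a "randomized controlled, parallel group study".

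The measurements are scheduled in both arms. The screening visit (2.3.1) includes "Intima-media thickness-IMT, Flow-Mediated Dilatation -FMD and Laser Doppler Flowmetry- LDF" for every participant, before randomisation. In section 2.3.2 the last MDI/CSII visit (Visit 8) includes "vascular status : Intima-media thickness-IMT, Flow-Mediated Dilatation -FMD and Laser Doppler Flowmetry- LDF", and the last AHCL visit (Visit 10, month 12) includes "blood sample for HbA1c lab test, vascular status : Intima-media thickness-IMT" with FMD and LDF.

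Section 7 sets out an analysis for time in range only. There the plan is to "compare the mean TIR between the randomized arms of the study. The analysis will be adjust by baseline TIR".

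**The concern.** The objective asks about the effect of a treatment. A before-after difference does not isolate that effect. Over a year in people over 65, vascular measures may move through ageing, trial attention or repeat testing, whatever the treatment. A shared improvement could be credited to AHCL, and a shared decline could hide a real benefit. The randomised control arm exists to take out such change, and its vascular data are already to be collected. Followed literally, the endpoint does not use them.

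**Working it through.** **1. Wording count (section 2.6).** 1 primary + 8 secondary lines = 9. Between-group wording: the primary, participants above 70% time in range, time in the glucose ranges, mean glucose, variability, HbA1c and quality of life = 7. The other two are the vascular line (time contrast) and physical capacity (no contrast). The vascular line is the only one that names a different contrast.

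**2. What each contrast estimates.** Let D be the AHCL effect and c the change common to both arms.
- Before-after in the AHCL arm: D + c. The bias is c, whatever test is used.
- Between arms: (D + c) − c = D, provided that c is the same in both arms.

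**3. Is c the same in both arms as scheduled?** Not fully, on the text of section 2.3.2. The control arm's Visit 8 is set six days (± 1) after Visit 6, and Visit 6 is at month 9, whereas the AHCL arm is measured at month 12. If Visit 7 was meant (month 12 minus 14 days), the control measurement falls 14 − 6 = 8 days before month 12. The AHCL arm also has two additional visits, so attention is not wholly shared.

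**4. The plan's own figure.** The protocol gives no size for the vascular endpoint. Its N = 40 for time in range reproduces: d = 15/15 = 1, two-sided 0.05, 80% power gives 16.7, so 17 per arm; 34/0.85 = 40. Hence 40 × 0.85 / 2 = 17 analysed per arm.

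**5. Illustration.** The protocol gives no test, drift, SD or correlation for this endpoint. Assumed here: a paired t-test in the AHCL arm, n = 17, two-sided 0.05, no AHCL effect, baseline-end correlation r, drift in SD of the measurement. SD of change = √(2(1 − r)) = 1.00, 0.77, 0.63 for r = 0.5, 0.7, 0.8. Noncentrality = drift × √17 / SD of change; at drift 0.3 and r = 0.5 this is 0.3 × 4.123 / 1.00 = 1.24.

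| Drift | r = 0.5 | r = 0.7 | r = 0.8 |
|---|---|---|---|
| 0 | 2.5% | 2.5% | 2.5% |
| 0.1 SD | 5.8% | 7.2% | 8.9% |
| 0.3 SD | 21.3% | 32.3% | 45.2% |

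Entries are the probability of significance in the drift's direction. Conversely, a benefit of 0.3 SD with an opposite drift of 0.3 SD nets to zero, and improvement is declared in 2.5% of trials. In simulation with an equal drift of ±0.3 SD in both arms and no effect, the between-arm estimate stayed within 0.002 SD of zero and rejected in 4.9% to 5.1% of trials, both with baseline adjustment and with change scores.

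**6. Price in precision.** Approximate 95% half-widths in SD, 17 per arm:

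| Contrast | Formula | r = 0.5 | r = 0.7 | r = 0.8 |
|---|---|---|---|---|
| Between arms, baseline-adjusted | t × √(2(1 − r²)/17) | 0.61 | 0.50 | 0.42 |
| Between arms, change scores | t × √(2 × 2(1 − r)/17) | 0.70 | 0.54 | 0.44 |
| Within one arm | t × √(2(1 − r)/17) | 0.51 | 0.40 | 0.33 |

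**The case against.** The line can be read as naming the participant-level variable, change over the study, with the comparison of arms supplied by the parallel-group design. Measuring the controls at the end points the same way. The line names no arm and no test, and nothing in the protocol rules out a between-arm comparison. The physical-capacity line and the three safety lines also lack between-group wording, so its absence alone is weak evidence. A statistical analysis plan, not shown here, may settle the contrast.

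Much of this stands. A reader might infer that the protocol commits to a before-after analysis of the AHCL arm alone; it does not. What remains is that the vascular line does more than omit a contrast: it states one, and that contrast is time. No other section corrects it, and an analysis plan written to the protocol would start from those words.

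A reader might also infer that the controls are measured at the same times, so that rewording alone removes all shared change. The visit text does not support that (step 3). Nor can the percentages be taken as demonstrated harm, since drift, correlation and test are all assumed.

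**Conclusion.** The concern holds as a poorly fixed contrast in one secondary endpoint. Taken literally, the line gives a result biased by exactly the change common to both arms, in either direction, and cannot answer the treatment question in section 2.1. That conclusion needs no assumed figure. The 6% to 45% range for drifts of 0.1 to 0.3 SD is illustration only and rests on 17 analysed per arm, r of 0.5 to 0.8 and a paired test that the protocol does not name. Confidence is medium, because the shorthand reading remains open. A between-arm comparison removes shared time-related change fully only if both arms are measured at the same time point. The primary analysis and N = 40 are unaffected. The correction should be made, since the endpoint serves part of the stated primary objective.

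**What to change.** Reword the line in section 2.6 as: Between-group difference in end-of-study IMT, FMD and LDF, adjusted for the baseline value. This follows the baseline adjustment in section 7. A between-group difference in change from baseline would also do. Report it with a 95% confidence interval and keep within-arm changes as description only.

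Reconcile the control arm's final-visit timing in section 2.3.2 with the AHCL arm's month 12 visit, so that the end-of-study time point is the same in both arms.

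The cost is one endpoint line and a correction to the visit text, with no additional vascular assessments or patients. The interval is wider than a within-arm one: about 0.42 to 0.61 SD half-width with baseline adjustment, against 0.33 to 0.51 SD, under the assumptions above.
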